DSAD discontinuation rate has been higher than expected. The screening and enrollment numbers require increasing in order to reach the objective of the study.

Section Number and Name	Description of Change	Brief Rationale
Section 1.1 Synopsis	Increased number of patients enrolled	Number of patients required increasing to ensure the objective of the study is met
Section 5.2 Exclusion Criteria	Exclusion Criterion 12, added HS wording	Clarification of prohibited concomitant therapy
	Exclusion Criterion 16, the sites should use the 14 day/baseline (randomization) visit timing, not relative to the screening visit	Clarification of prohibited concomitant therapy
	Exclusion Criterion 35, hemoglobin level corrected to 90.0 g/L	Error correction
Section 6.5.1 Washout Period Before Enrollment	Added HS wording	Clarification of prohibited concomitant therapy
Section 6.5.4 Prohibited Concomitant Therapy	Added HS wording	Clarification of prohibited concomitant therapy rules
Section 8.1.1.2 Modified Sartorius Score (mSS)	Lesion distance corrected	Error correction
Section 8.1.6 Patient's Global Impression of Severity – 7 Days (Hidradenitis Suppurativa)	Clarified scoring system	Changed to match Patient's Global Impression of Severity form

Removed "at or" wording before the age of 40 years	To clarify that in reference it is <40
the age of 40 years	and not <=40
Number of patients enrolled increased	Number of patients required increasing to ensure the objective of the study is met
Electronic data collection is not occurring Correction of SAE reporting	Correction
N ir E	Tumber of patients enrolled nereased lectronic data collection is not

Table of Contents

1.	Protocol Summary	8
1.1.	Synopsis	
1.2.	Schema	
1.3.	Schedule of Activities (SoA)	11
2.	Introduction	24
2.1.	Study Rationale	24
2.2.	Background	24
2.3.	Benefit/Risk Assessment	24
3.	Objectives and Endpoints	26
4.	Study Design	27
4.1.	Overall Design.	27
4.2.	Scientific Rationale for Study Design	27
4.2.1.	Participant Input into Design	28
4.3.	Justification for Dose	28
4.4.	End-of-Study Definition	29
5.	Study Population	30
5.1.	Inclusion Criteria	30
5.2.	Exclusion Criteria	31
5.3.	Lifestyle Considerations	35
5.4.	Screen Failures	35
5.4.1.	Allowed Retesting of Screening Investigations	35
5.4.2.	Rescreening of Individuals Who Failed Screening	35
6.	Study Intervention	37
6.1.	Study Interventions Administered	
6.2.	Preparation/Handling/Storage/Accountability	37
6.3.	Measures to Minimize Bias: Randomization and Blinding	

1.1. Synopsis

Protocol Title: A Multicenter, Randomized, Double-Blind, Placebo-Controlled, Phase 2 Study to Evaluate the Efficacy and Safety of LY3041658 in Adults with Moderate-to-Severe Hidradenitis Suppurativa

Rationale: LY3041658 is a humanized immunoglobulin G (IgG) 4-variant monoclonal antibody (mAb) that binds to and neutralizes all 7 of the known ligands (referred to collectively as ELR+ [E = glutamic acid, L = leucine, R = arginine] chemokines) that signal through the human chemokine, CXC motif, receptors 1 and 2 (CXCR1 and CXCR2). LY3041658 binds to an epitope that is common to all 7 ELR+ chemokines. Signaling through CXCR1 and CXCR2 modulates neutrophil migration and angiogenesis, and neutrophil migration into sites of inflammation is critical to the pathogenesis of hidradenitis suppurativa (HS). Thus, LY3041658 is being developed for the treatment of HS. This proof-of-concept study will evaluate the safety and efficacy of LY3041658 in adults with HS.

Objectives and Endpoints

Objectives	Endpoints
Primary	
To test the hypothesis that treatment with LY3041658 is superior to placebo in inducing Hidradenitis Suppurativa Clinical Response (HiSCR) in adult participants with moderate-to- severe hidradenitis suppurativa (HS)	Proportion of participants achieving HiSCR response at Week 16
Secondary	
To evaluate the efficacy of LY3041658 compared to placebo with respect to measures of signs and symptoms and pain in adult participants with moderate-to-severe HS	 Mean change from baseline to Week 16 in: Total number of abscesses and inflammatory nodules (AN count) Skin Pain – HS Numeric Rating Scale (NRS)

Note: HiSCR is defined as at least a 50% reduction in the total abscess and inflammatory nodule count (AN count) with no increase in abscess count and no increase in draining fistulae count relative to baseline.

Overall Design

Study I7P-MC-DSAD (DSAD) is a multicenter, randomized, double-blind, placebo-controlled, parallel-group Phase 2 study to evaluate the efficacy and safety of LY3041658 600 mg given intravenously (IV) every 2 weeks (Q2W) in adults with HS.

The study duration will be up to approximately 51 weeks over 4 study periods:

Screening: a period lasting up to 35 days before Week 0 (Visit 2, baseline)

Treatment Period 1: a 16-week, 2-group double-blind treatment period

Treatment Period 2: a 20-week, single-group open-label extension period, and

Post-treatment follow-up: a period lasting approximately 10 weeks.

Topical antiseptics will be required as concomitant therapy during the study. Participants who were on stable doses of oral antibiotics at screening will remain on the same stable dose throughout the study.

Disclosure Statement: In this study, the 2-arm parallel treatment period is participant-blinded and investigator-blinded and is followed by a single-arm open-label extension treatment period.

Number of Participants: Approximately 100 patients will be screened to achieve approximately 63 randomized participants.

Intervention Groups and Duration:

[figure not shown]
At baseline, participants will be randomized in a 2:1 ratio to one of two treatments groups:

Approximately 42 participants will receive LY3041658 600 mg IV Q2W for 16 weeks, and Approximately 21 participants will receive placebo IV Q2W for 16 weeks.

Starting at Week 16, all participants, including those previously assigned to placebo, will receive LY3041658 600 mg IV Q2W for 20 weeks.

Data Monitoring Committee: No

1.2. Schema

Note: Starting at Week 16 participants who received placebo in Treatment Period 1 will receive LY3041658 600 mg IV Q2W.

Abbreviations: FD = first dose; IV = intravenous; LD = last dose; Q2W = every 2 weeks; R = randomization visit; V = visit; W = study week relative to randomization visit.

Figure 1. Schema of Study I7P-MC-DSAD, a Phase 2 study to evaluate the efficacy and safety of LY3041658 in adults with moderate-to-severe hidradenitis suppurativa.

1.3. Schedule of Activities (SoA)

Table 1. Schedule of activities for the Screening Period and Treatment Period 1 of Study I7P-MC-DSAD

Visit 1 procedures may be conducted over more than 1 day as long as all activities are completed within the allowable visit tolerance.

For procedures at an early termination visit, see ETV in Table 2.

For procedures at an unscheduled visit, see V997 in Table 2. Unscheduled visits are for participants needing rescue therapy or incision and drainage.

For procedures at an unscheduled	visit, s	ee v 95	9 / IN I	abie 2.	Unsch	eduled	i visits	are 101	partic	ipants n	needing rescue therapy or incision and drainage.
Visit number	V1	V2	V3	V4	V5	V6	V7	V8	V9	V10	Comment
Weeks from randomization	-5	_	2	4	6	8	10	12	14	16	
Study day	—	1	15	29	43	57	71	85	99	113	
Visit interval tolerance (days)	≤35	_	±2	±2	±2	±2	±2	±2	±2	±2	
Fasting visit		X								X	
Informed consent	X										
Inclusion and exclusion criteria, review and confirm	X	X									
Demographics	X										
Preexisting conditions and medical history	X										
Prespecified medical history (indication and history of interest)	X										
Prior treatments for indication	X										Relevant surgical history
Concomitant medications	X	X	X	X	X	X	X	X	X	X	
Adverse events	X	X	X	X	X	X	X	X	X	X	For AESIs, additional data are collected (Section 8.3.6).
Substance use (alcohol, caffeine, tobacco)	X										
Surgical interventions related to HS		X	X	X	X	X	X	X	X	X	
Physical Evaluation											
Height	X										Without shoes.
Weight	X									X	
Vital signs	X	X	X	X	X	X	X	X	X	X	Blood pressure, body temperature, pulse rate. Vital signs should be measured after participant has been sitting for at least 5 minutes.

Table 1. Schedule of activities for the Screening Period and Treatment Period 1 of Study I7P-MC-DSAD

Visit 1 procedures may be conducted over more than 1 day as long as all activities are completed within the allowable visit tolerance.

For procedures at an early termination visit, see ETV in Table 2.

For procedures at an unscheduled visit, see V997 in Table 2. Unscheduled visits are for participants needing rescue therapy or incision and drainage.											
Visit number	V1	V2	V3	V4	V5	V6	V7	V8	V9	V10	Comment
Weeks from randomization	-5	_	2	4	6	8	10	12	14	16	
Study day	_	1	15	29	43	57	71	85	99	113	
Visit interval tolerance (days)	≤35	_	±2	±2	±2	±2	±2	±2	±2	±2	
Fasting visit		X								X	
Physical examination	X										The complete physical exam will exclude pelvic, rectal, and breast exams and will include assessment for signs and symptoms of tuberculosis (TB), including peripheral lymph nodes (Section 8.2.2).
Symptom-directed physical examination		X	X	X	X	X	X	X	X	X	See Section 8.2.2.
12-lead ECG (local)	X									X	
Chest x-ray (posterior-anterior view) (local)	X										Interpreted and reported by radiologist or pulmonologist. Not performed at screening if performed within 6 months before screening and if qualifying radiographs or equivalent imaging study and/or formal report are available for investigator's review and sufficient for TB evaluation according to local standard of care (Section 8.2.4).
Patient-Reported Outcomes (El	ectroni		1	ı	ı					ı	
DLQI		X		X		X		X		X	
Skin Pain – HS NRS		X	X	X	X	X	X	X	X	X	
Drainage NRS		X	X	X	X	X	X	X	X	X	
Smell NRS		X	X	X	X	X	X	X	X	X	
Patient's Global Impression of Severity – 7 Days (Hidradenitis Suppurativa)		X	X	X	X	X	X	X	X	X	
Patient Global Impression of Change – 7 Days (Hidradenitis Suppurativa)		X						X		X	

Table 1. Schedule of activities for the Screening Period and Treatment Period 1 of Study I7P-MC-DSAD

Visit 1 procedures may be conducted over more than 1 day as long as all activities are completed within the allowable visit tolerance.

For procedures at an early termination visit, see ETV in Table 2.												
For procedures at an unscheduled	visit, s	ee V99	97 in T	able 2.	Unsch	edule	l visits	are for	r partic	ipants n	needing rescue therapy or incision and drainage.	
Visit number	V1	V2	V3	V4	V5	V6	V7	V8	V9	V10	Comment	
Weeks from randomization	-5	—	2	4	6	8	10	12	14	16		
Study day	—	1	15	29	43	57	71	85	99	113		
Visit interval tolerance (days)	≤35	_	±2	±2	±2	±2	±2	±2	±2	±2		
Fasting visit		X								X		
Patient-Reported Outcomes (Paper)												
Spinal Pain NRS		X								X	See Section 8.1.8.	
Clinician-Administered Question	nnaire	s (Ele	ctroni	c)								
Lesion assessments	X	X	X	X	X	X	X	X	X	X	Includes anatomical region, type and number (see Section 8.1.1).	
Hurley stage	X	X										
Clinician-Administered Question	nnaire	s (Pap	er)									
C-SSRS Screening/Baseline	X											
C-SSRS Since Last Visit		X	X	X	X	X	X	X	X	X		
Self-Harm Supplement Form	X	X	X	X	X	X	X	X	X	X		
Self-Harm Follow-Up Form	X	X	X	X	X	X	X	X	X	X	Required if triggered by the Self-Harm Supplement Form per instructions.	
Inflammatory Back Pain Assessment (ASAS Expert Criteria)		X									See Section 8.1.8.	
Laboratory Tests and Sample C	ollecti	ons										
Hematology	X	X	X	X	X	X	X	X	X	X		
Clinical chemistry	X	X	X	X	X	X	X	X	X	X		
Lipid panel		X								X	Participants should not eat or drink anything but water for 12 hours before the visit. Fasting is not required at an ETV. If a participant attends these visits in a nonfasting state, the sample should still be collected. This will not be considered a protocol violation.	
Urinalysis	X	X								X		

Table 1. Schedule of activities for the Screening Period and Treatment Period 1 of Study I7P-MC-DSAD

Visit 1 procedures may be conducted over more than 1 day as long as all activities are completed within the allowable visit tolerance.

For procedures at an early termination visit, see ETV in Table 2.

For procedures at an unscheduled visit, see V997 in Table 2. Unscheduled visits are for participants needing rescue therapy or incision and drainage.

	 		1	1				1		1	
Visit number	V1	V2	V3	V4	V5	V6	V7	V8	V9	V10	Comment
Weeks from randomization	-5	—	2	4	6	8	10	12	14	16	
Study day	—	1	15	29	43	57	71	85	99	113	
Visit interval tolerance (days)	≤35	_	±2	±2	±2	±2	±2	±2	±2	±2	
Fasting visit		X								X	
Serum pregnancy	X										Only for WOCBP (Section 8.2.5.1, Appendix 10.4) and women with a history of tubal ligation. Central laboratory.
Urine pregnancy (local)		X	X	X	X	X	X	X	X	X	Only for WOCBP (Section 8.2.5.1, Appendix 10.4) and women with a history of tubal ligation. Result must be negative before dosing at each dosing visit.
Follicle-stimulating hormone (FSH)	X										Optional, performed to confirm postmenopausal status (Section 8.2.5.1)
Tuberculosis (TB) test	X										Patients who had a tuberculin skin test (TST) will return from 48 to 72 hours after placement to have their test results read (Section 8.2.6). Samples may be sent to a central or local laboratory based on the type of test. A local laboratory must be qualified by local regulations.
HIV screening tests	X										
Hepatitis C virus (HCV) screening tests	X										HCV RNA will be measured to confirm positive hepatitis C virus antibody (Section 8.2.8).
Hepatitis B virus (HBV) screening tests	X										Includes testing for HBsAg and anti-HBc (Section 8.2.7)
C-reactive protein, high-sensitivity (hs-CRP)		X		X				X		X	
IL-8		X	X			X				X	
Total immunoglobulins (IgA, IgE, IgG, and IgM)		X								X	If a hypersensitivity event occurs, collect additional samples (see Appendix 10.2, Section 10.2.2).

Table 1. Schedule of activities for the Screening Period and Treatment Period 1 of Study I7P-MC-DSAD

Visit 1 procedures may be conducted over more than 1 day as long as all activities are completed within the allowable visit tolerance.

For procedures at an early termination visit, see ETV in Table 2.

For procedures at an unscheduled visit, see V997 in Table 2. Unscheduled visits are for participants needing rescue therapy or incision and drainage.

Tor procedures at all unschedured	V1511, 5	CC V 93	7 / 111 1	able 2.	Uliscii	caurec	1 112112	are 10	partic	ipanis n	leeding rescue therapy or incision and dramage.
Visit number	V1	V2	V3	V4	V5	V6	V7	V8	V9	V10	Comment
Weeks from randomization	-5	_	2	4	6	8	10	12	14	16	
Study day	_	1	15	29	43	57	71	85	99	113	
Visit interval tolerance (days)	≤35	—	±2	±2	±2	±2	±2	±2	±2	±2	
Fasting visit		X								X	
Pharmacokinetic (PK) sample		X	X	X		X		X		X	At Visit 2, Visit 10, and Visit 19, collect samples at 3 time points:
											If a hypersensitivity event occurs, collect additional samples (see (Appendix 10.2, Section 10.2.2).
Immunogenicity (ADA) sample		X		X						X	Collect samples before dosing, if dosing is scheduled. If a hypersensitivity event occurs, collect additional samples (see Appendix 10.2, Section 10.2.2). See Section 8.9 for additional details.
Exploratory biomarker sample – Whole blood for RNA and for epigenetics,		X		X						X	
Pharmacogenetics sample (DNA)	X										
Exploratory biomarker samples - other		X	X	X		X		X		X	At Visit 2 and Visit 10, collect samples before the infusion starts.
Randomization and dosing											
Randomization		X									
Dosing		X	X	X	X	X	X	X	X	X	No dosing at Visit 1, Visit 20, ETV, or V997.

Abbreviations: ADA = anti-drug antibody; AESI = adverse event of special interest; anti-HBc = antibody to hepatitis B core antigen; ASAS = Assessment of SpondyloArthritis International Society; C-SSRS = Columbia Suicide-Severity Rating Scale; DLQI = Dermatology Life Quality Index; DNA = deoxyribonucleic acid; ECG = electrocardiogram; ETV = early termination visit; HBsAg = hepatitis B surface antigen; HIV = human immunodeficiency virus; HS = hidradenitis suppurativa; NRS = numeric rating scale; RNA = ribonucleic acid; V = visit; WOCBP = women of childbearing potential.

Table 2. Schedule of activities for Treatment Period 2 of Study I7P-MC-DSAD

For procedures at an early termination visit, see ETV in Table 2.

For procedures at an unscheduled visit, see V997 in Table 2. Unscheduled visits are for participants needing rescue therapy or incision and drainage.

For procedures at an unschedu	ilea visi	t, see v	99 / In .	i abie 2.	Unsch	eaurea v	isits are	e for par	ticipan	is needii	ng rescu	ie therap	y or incision and drainage.
Visit number	V11	V12	V13	V14	V15	V16	V17	V18	V19	V20	ETV	V997	Comment
Week from randomization	18	20	22	24	26	28	30	32	34	36		—	
Study day	127	141	155	169	183	197	211	225	239	253	_	_	
Visit interval tolerance													
(days)	±2	±2	±2	±2	±2	±2	±2	±2	±2	±2	_	_	
Fasting visit										X			
Concomitant medications	X	X	X	X	X	X	X	X	X	X	X	X	
Adverse events	X	X	X	X	X	X	X	X	X	X	X	X	For AESIs, additional data are collected (Section 8.3.6).
Surgical interventions related to HS	X	X	X	X	X	X	X	X	X	X	X	X	
Physical Evaluation													
Weight										X	X		
Vital signs	X	X	X	X	X	X	X	X	X	X	X	X	Blood pressure, body temperature, pulse rate. Vital signs should be measured after participant has been sitting for at least 5 minutes.
Symptom-directed physical examination	X	X	X	X	X	X	X	X	X	X	X	X	See Section 8.2.2.
12-lead ECG (local)										X	X		
Patient-Reported Outcomes	(Electr	onic)											
DLQI				X				X		X	X		
Skin Pain – HS NRS		X		X		X		X		X	X	X	
Drainage NRS		X		X		X		X		X	X	X	
Smell NRS		X		X		X		X		X	X	X	
Patient's Global Impression of Severity – 7 Days (Hidradenitis Suppurativa)		X		X		X		X		X	X	X	

Table 2. Schedule of activities for Treatment Period 2 of Study I7P-MC-DSAD For procedures at an early termination visit, see ETV in Table 2. For procedures at an unscheduled visit, see V997 in Table 2. Unscheduled visits are for participants needing rescue therapy or incision and drainage. V11 V12 V14 V17 V19 **V20** ETV V997 Visit number V13 V15 V16 V18 Comment Week from randomization 22 24 26 28 34 36 18 20 30 32 127 141 155 169 183 197 211 225 239 253 Study day Visit interval tolerance ± 2 (days) X **Fasting visit** Patient Global Impression of Χ X X Change – 7 Days (Hidradenitis Suppurativa) **Patient-Reported Outcomes (Paper)** X Spinal Pain NRS X See Section 8.1.8. **Clinician-Administered Questionnaires (Electronic)** X X Includes anatomical region, type Lesion assessments X X X X X X X X X X and number (see Section 8.1.1). Clinician-Administered Questionnaires (Paper) X X X X X C-SSRS Since Last Visit X X X X X X X Self-Harm Supplement X X X X X X X X X X X X Form Self-Harm Follow-Up Form X X X X X X X X X X Required if triggered by the X X Self-Harm Supplement Form per instructions. **Laboratory Tests and Sample Collections** Hematology X X X X \mathbf{X} X X X X X Χ X X X X X X X X Clinical chemistry X X X

Table 2. Schedule of activities for Treatment Period 2 of Study I7P-MC-DSAD

For procedures at an early termination visit, see ETV in Table 2.

For procedures at an unscheduled visit, see V997 in Table 2. Unscheduled visits are for participants needing rescue therapy or incision and drainage.

For procedures at an unschedu		ĺ											
Visit number	V11	V12	V13	V14	V15	V16	V17	V18	V19	V20	ETV	V997	Comment
Week from randomization	18	20	22	24	26	28	30	32	34	36	—	_	
Study day	127	141	155	169	183	197	211	225	239	253			
Visit interval tolerance													
(days)	±2	±2	±2	±2	±2	±2	±2	±2	±2	±2	—	_	
Fasting visit										X			
Lipid panel										X	X		Participants should not eat or drink
													anything but water for 12 hours
													before the visit. Fasting is not
													required at an ETV. If a participant
													attends these visits in a nonfasting
													state, the sample should still be
													collected. This will not be
													considered a protocol violation.
Urinalysis										X	X		•
Urine pregnancy (local)	X	X	X	X	X	X	X	X	X	X	X		Only for WOCBP (Section 8.2.5.1,
, ,													Appendix 10.4) and women with a
													history of tubal ligation. Result
													must be negative before dosing at
													each dosing visit.
C-reactive protein,										X	X		Ç
high-sensitivity (hs-CRP)													
IL-8	X				X					X	X		
Total immunoglobulins										X	X		If a hypersensitivity event occurs,
(IgA, IgE, IgG, and IgM)										1.	1.		collect additional samples (see
(15/1, 152, 153, and 15/1)													Appendix 10.2, Section 10.2.2).
				l				l	l	l			Appendix 10.2, Section 10.2.2).

Table 2. Schedule of activities for Treatment Period 2 of Study I7P-MC-DSAD

For procedures at an early termination visit, see ETV in Table 2.

For procedures at an unscheduled visit, see V997 in Table 2. Unscheduled visits are for participants needing rescue therapy or incision and drainage.													
Visit number	V11	V12	V13	V14	V15	V16	V17	V18	V19	V20	ETV	V997	Comment
Week from randomization	18	20	22	24	26	28	30	32	34	36			
Study day	127	141	155	169	183	197	211	225	239	253	_	_	
Visit interval tolerance													
(days)	±2	±2	±2	±2	±2	±2	±2	±2	±2	±2		_	
Fasting visit										X			
Pharmacokinetic (PK) sample	X	X			X			X	X	X	X		At Visit 2, Visit 10, and Visit 19, collect samples at 3 time points: If a hypersensitivity event occurs, collect additional samples (see (Appendix 10.2, Section 10.2.2).
Immunogenicity (ADA) sample Exploratory biomarker samples - other		X			X			X		X	X		Collect samples before dosing, if dosing is scheduled. If a hypersensitivity event occurs, collect additional samples (see Appendix 10.2, Section 10.2.2). See Section 8.9 for additional details.
Dosing	l	l .	l	1	l	l	l	l .			l .	 	l
Dosing	X	X	X	X	X	X	X	X	X				No dosing at Visit 1, Visit 20, ETV, or V997.

Abbreviations: ADA = anti-drug antibody; AESI = adverse event of special interest; C-SSRS = Columbia Suicide-Severity Rating Scale; DLQI = Dermatology Life Quality Index; ECG = electrocardiogram; ETV = early termination visit; HS = hidradenitis suppurativa; NRS = numeric rating scale; V = visit; WOCBP = women of childbearing potential.

Table 3. Schedule of activities for the Post-Treatment Follow-Up Period of Study I7P-MC-DSAD For procedures at an early termination visit, see ETV in Table 2. For procedures at an unscheduled visit, see V997 in Table 2. Unscheduled visits are only for participants needing rescue therapy or incision and drainage. V802 Visit number V801 **Comment** 40 or 46 or Week relative to randomization ETV+4 ETV+10 323 Study day 281 Visit interval tolerance (days) ±7 ±7 Fasting visit No fasting in this period. X Concomitant medications X X X For AESIs, additional data are collected (Section 8.3.6). Adverse events Surgical interventions related to HS X X **Physical Evaluation** Blood pressure, body temperature, pulse rate. Vital signs should be measured after X X participant has been sitting for at least 5 minutes. Vital signs Symptom-directed physical examination X X See Section 8.2.2. **Patient-Reported Outcomes (Electronic)** Skin Pain - HS NRS X X X X Drainage NRS X Smell NRS X Patient's Global Impression of Severity – X 7 Days (Hidradenitis Suppurativa) X **Patient-Reported Outcomes (Paper)** Spinal Pain NRS Χ See Section 8.1.8. **Clinician-Administered Questionnaires (Electronic)** Lesion assessments Χ Χ Includes anatomical region, type and number (see Section 8.1.1). Clinician-Administered Questionnaires (Paper) C-SSRS Since Last Visit X X Self-Harm Supplement Form X X Χ Self-Harm Follow-Up Form Χ Required if triggered by the Self-Harm Supplement Form per instructions. **Laboratory Tests and Sample Collections** Hematology X X

X

X

Clinical chemistry

Table 3. Schedule of activities for the Post-Treatment Follow-Up Period of Study I7P-MC-DSAD

For procedures at an early termination visit, see ETV in Table 2.

For procedures at an unscheduled visit, see V997 in Table 2. Unscheduled visits are only for participants needing rescue therapy or incision and drainage.

Visit number	V801	V802	Comment
	40 or	46 or	
Week relative to randomization	ETV+4	ETV+10	
Study day	281	323	
Visit interval tolerance (days)	±7	±7	
Fasting visit			No fasting in this period.
			Only for WOCBP (Section 8.2.5.1 and Appendix 10.4) and women with a history of
Urine pregnancy (local)	X	X	tubal ligation.
C-reactive protein, high-sensitivity (hs-CRP)		X	
			If a hypersensitivity event occurs, collect additional samples (see Appendix 10.2,
Pharmacokinetic (PK) sample X		X	Section 10.2.2).
			If a hypersensitivity event occurs, collect additional samples (see Appendix 10.2,
Immunogenicity (ADA) sample		X	Section 10.2.2). See Section 8.9 for additional details.
Dosing			No dosing in this period

Abbreviations: ADA = anti-drug antibody; AESI = adverse event of special interest; C-SSRS = Columbia Suicide-Severity Rating Scale; ETV = early termination visit; HS = hidradenitis suppurativa; NRS = numeric rating scale; V = visit; WOCBP = women of childbearing potential.

2. Introduction

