#### **6.9.3. Clinical Laboratory Evaluation**

Laboratory analyses will include planned analytes only. Planned analytes are those specified in the protocol. Summaries will be provided in both Système International (SI) and United States (US) conventional (CN) units (when different). Limits from the performing lab will be used to define low and high. Analyses of laboratory values will be produced using the measurements collected at scheduled time points. All unscheduled assessments will appear only in data listings.

- **Box plots for observed values:** Values at each visit (starting at randomization) will be displayed in box plots for patients who have both a baseline and a result for the specified visit. Unplanned measurements will be excluded. Original-scale data will be used for the display. These box plots will be used to evaluate trends over time and to assess a potential impact of outliers on central tendency summaries. The box plot will be a notched box for each treatment with outliers displayed, individual measurements outside

of reference limits will also be displayed using distinct symbols overlaying the box plot, and descriptive summary statistics will be included in a table below the box plot.

- Box plots for change values:** Change from baseline to each visit will be displayed in box plots for patients who have both a baseline and a result for the specified visit. Change from baseline to last observation will also be summarized and analyzed for patients who have both baseline and at least 1 postbaseline result. Baseline will be the last non-missing observation in the baseline period. The last non-missing observation in the Dosing Period will be used as the last observation. Unplanned measurements will be excluded. The box plot will be a notched box for each treatment with outliers displayed, change from baseline to last observation will be summarized within the box plot of changes (rightmost column), and descriptive summary statistics will be included in a table below the box plot, along with a p-value using the ANCOVA model containing terms for treatment and the continuous covariate of baseline measurement. Type III sums of squares will be used. The significance of within-treatment group changes from baseline will be evaluated by testing whether the treatment group LSMeans changes from baseline are different from zero using a t-statistic. In addition to the LSMeans and tests, the SD, minimum, Q1, median, Q3, and maximum will be displayed.

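### SAP 6.9.3 tests within-arm glucose change without regard to fasting, so 8 of 18 post-baseline visits compare a fasting-visit value with one taken where fasting is not required

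*Protocol*

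**What the plan says.** **Fasting visits.** In Protocol 1.3, Table 1 marks two visits as fasting, V2 and V10 ("Fasting visit X X"). Table 2 marks one, V20 ("Fasting visit X"). The fast is 12 hours with water only. For the lipid panel the comment adds: "Fasting is not required at an ETV. If a participant attends these visits in a nonfasting state, the sample should still be collected". Nonfasting attendance is not treated as a protocol violation.

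**What is drawn when.** Chemistry is drawn at every visit from V1 to V10 ("Clinical chemistry X X X X X X X X X X"). The Table 2 row is broken in the text available but reads as V11 to V20 plus the ETV. Appendix 10.2.1 lists glucose in that panel. The lipid panel is drawn only at V2, V10, V20 and the ETV.

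**Baseline.** SAP 6.3.2 takes the last nonmissing value up to first dosing for Period 1, and the last value available before Visit 10 for Period 2. SAP 6.9 applies these definitions to safety data.

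**Analysis.** SAP 6.9.3 compares each visit and the last observation with baseline for the planned analytes, and evaluates each arm by "testing whether the treatment group LSMeans changes from baseline are different from zero using a t-statistic". On the last observation it says: "The last non-missing observation in the Dosing Period will be used as the last observation". SAP 6.3.3 adds the comparison with placebo and treatment-emergent high or low results. The SAP does not mention fasting.

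**The concern.** The protocol imposes a 12-hour fast at three visits, yet the analysis makes no use of the distinction. A within-arm test of glucose change assumes that both values were taken under like conditions. If the baseline follows a fast and the later value does not, the mean change contains a food effect that the test cannot separate from a drug effect. A treatment-emergent high glucose can arise in the same way.

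The reverse also matters. If the baseline was taken without a fast and the end-of-treatment value after one, food pulls the change down and may mask a real increase. That is the position at V20, in an open-label period with no control arm to expose it.

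At stake are the glucose tables of the safety report and, to a smaller degree, the lipid last-observation summary. No efficacy result depends on them.

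**Working it through.** The documents give no figure on this point, so there is nothing of the plan's own to reproduce.

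**Step 1. Count mismatched glucose visits against the SAP's own baselines.** Post-baseline treatment visits are V3 to V20, which is 18.

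| Period | Usual glucose baseline | Visits that match | Visits that do not |
|---|---|---|---|
| 1 (V3 to V10) | V2, fasting | V10 | V3 to V9: 7 of 8 |
| 2 (V11 to V20) | V9, fasting not required | V11 to V19 | V20: 1 of 10 |

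Total: 7 + 1 = 8 of 18. If Period 2 is read against V2 instead, V11 to V19 mismatch and V20 matches: 7 + 9 = 16 of 18.

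**Step 2. Direction.** Let the food shift be *s* and the true change be *c*. At V3 to V9 the expected observed change is *c* + *s*. At V20 against V9 it is *c* − *s*. With *s* = 0.4 mmol/L (an assumption), a true rise of 0.4 at V20 would appear as 0.4 − 0.4 = 0.

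**Step 3. Size at one mismatched Period 1 visit.** Inputs from the documents: two-sided alpha 0.05 (SAP 6.3), and 42 and 21 participants per arm (Protocol 9.2). Assumptions, not in the documents: food shift 0.2, 0.4 or 0.6 mmol/L, SD of change 0.8 to 1.2 mmol/L, everyone fed at the later visit, and no drug effect. The method is a one-sample t test with noncentrality (shift/SD) × √n and n − 1 degrees of freedom. For example, 0.4/0.8 = 0.5 and 0.5 × √42 = 3.24, giving 89%. Each range below runs from SD 1.2 to SD 0.8.

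| n | Shift 0.2 | Shift 0.4 | Shift 0.6 |
|---|---|---|---|
| 42 | 18–35% | 56–89% | 89–100% |
| 21 | 11–19% | 31–59% | 59–90% |
| 30 (42 × 45/63) | 14–26% | 42–75% | 75–98% |
| 15 (21 × 45/63) | 9–15% | 23–44% | 44–77% |

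The nominal rate is 5%. The last two rows apply the expected completion of 45 of 63 (Protocol 9.2) to each arm, to show the effect of dropout by late Period 1.

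**Step 4. Same-visit comparison with placebo.** Both arms share the schedule. A simulation of 20,000 trials at 42 versus 21, with the same shift of 0.3, 0.5 or 1.0 SD in both arms, gave p<0.05 in 4.9%, 5.3% and 5.0%. The between-arm test is not inflated.

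**Step 5. Lipids.** The two scheduled post-baseline samples, V10 and V20, and the V2 baseline are all at fasting visits, so 0 of 2 scheduled changes mix states by design. Mixing is possible through tolerated nonfasting attendance and, if ETV values count as the last observation, through the ETV. As an upper bound, 63 − 45 = 18 of 63 (28.6%) would supply a nonfasting ETV value. The mean shift is then 0.286 times the food effect. For assumed effects of 0.3, 0.5 and 1.0 SD that is 0.09, 0.14 and 0.29 SD, and the within-arm test at n=42 gives p<0.05 in about 8%, 14% and 38%.

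**The case against.** Several points on the other side stand.

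- **Randomised comparison.** SAP 6.3.3 reports the least-squares mean difference from placebo, and Step 4 shows that it keeps its error rate at a shared visit. A reader might infer that the Period 1 safety comparison with placebo is biased. At scheduled visits it is not.
- **Period 2.** A reader might infer that 16 of 18 visits are mismatched and that no Period 2 change can be separated from food. That holds only if Period 2 is read against V2. SAP 6.3.2 makes V9 the usual baseline, and V11 to V19 are taken under the same rule as V9.
- **Lipids.** A reader might extend the glucose problem to lipids. No lipid panel is scheduled at a visit without a fasting requirement.
- **ETV.** It is tempting to say that ETV values enter the last-observation change. SAP 6.9.3 uses scheduled time points, excludes unplanned measurements and takes the last value in the dosing period, while the ETV has no scheduled week and no dosing. The SAP does not settle the matter. The 18 of 63 is also a ceiling, because Protocol 7.2 asks for an ETV only where possible after study withdrawal.
- **Recording.** Neither document says that fasting status is captured, but Protocol 8.2.5 defers to a laboratory manual that is not available here. Its absence is not established.
- **Magnitude.** The food effects are assumed, and some participants may attend fasted where no fast is required.

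What these do not answer is the within-arm glucose test at V3 to V9 and the V20 change. Both follow from applying the plan as written.

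**Conclusion.** The point holds for within-arm glucose analyses at 8 of 18 visits, counted against the SAP's period baselines: V3 to V9 in Period 1, where food can produce an apparent rise, and V20 in Period 2, where it can hide one. For lipids the exposure is limited to tolerated nonfasting attendance and to ETV samples, the latter only if these count as the last observation. A last-observation comparison between arms could also be distorted, if ETV values enter it and early termination differs by arm.

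The 18 to 100% (n=42) and 11 to 90% (n=21) rejection rates illustrate the mechanism under assumed shifts and SDs with everyone fed. They are not predictions for this trial, and they fall somewhat after dropout.

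Severity is minor. Glucose and lipids are not endpoints, adverse events of special interest or special safety topics, and no decision rule uses them.

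**What to change.** In SAP 6.9.3:

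1. Report within-arm glucose tests, and last-observation change for glucose and lipids, only for fasting-to-fasting pairs (V2 to V10 and V2 to V20).
2. Keep the between-arm glucose comparison at V3 to V9, labelled as fasting not required.
3. Exclude nonfasting ETV glucose and lipids from last-observation change and list them separately.
4. Tabulate treatment-emergent high glucose and triglycerides by fasting status.
5. Record fasting yes or no at V2, V10, V20 and the ETV, unless the laboratory forms already do so.

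The cost is a few SAP sentences and one data item at four visits. The main downside is that fewer visits carry a within-arm glucose p-value. The V2-to-V20 pair also departs from the Period 2 baseline, which SAP 6.3.2 permits for supporting analyses; for participants first given placebo it spans both treatments, and the table should say so. A blanket restriction of all glucose analyses to fasting samples would be worse, because it would discard the valid placebo comparisons at V3 to V9 and push the Period 2 glucose baseline back to V2.
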